All subjects that are administered RTS,S or rabies vaccine will be observed for at least 30 minutes after vaccination to evaluate and treat any acute adverse events.

The first 50 subjects in groups 1 and 2 and all subjects in group 3 will constitute the Reactogenicity Cohort, which will be evaluated for solicited local and general adverse effects seven days after each immunization. Following each injection, the Reactogenicity Cohort will be provided a memory aid, instructed on its use, and encouraged to fill it out as directed. When field workers visit subjects on day 7 after each immunization, the field worker will review the memory aid document with the subject. The memory aid and/or the interview with the subject will be used to complete the CRF entries for solicited local and general AEs that have occurred on days 1 through day 7 post immunization. If the memory aid is not completed or not brought to a study visit by Day 28 following each dose, this will be documented in the CRF. Specifically, the Reactogenicity Cohort will be asked to:

- Record any local or general symptoms that they experience on a daily basis during the 7-day period after each injection in the memory aid.
- Record their temperatures daily in the memory aid for the first 7 days after each injection to help assess for possible fevers. To more accurately account for possible fevers, subjects will be given an oral thermometer and instructed on its use.
- Record local reactions at the injection sites in the memory aid for 7 days after each injection.

Subjects in Groups 4 and 5 will not have solicited AEs captured.

There will be a 28-day follow-up period after each dose of vaccine for reporting unsolicited symptoms in all subjects from all Groups and, where applicable, following each course of per protocol scheduled anti-malarial treatment (i.e. Groups 1, 2, 4 and 5).

Blood sampling for immunologic assays in selected groups of subjects at pre-defined timepoints will be collected as shown in Appendix F. For the determination of anti-rabies antibody levels, only the first 50 subjects each in Groups 4 and 5 will have blood samples collected for rabies antibody determination.

A urine pregnancy test will be performed prior to administering any vaccine or before each course of anti-malarial drug begins according to Appendix B.

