8.3. Time Period and Frequency of Event Assessment and Follow-up

All solicited local and systemic AEs occurring within 7 days following administration of each dose of vaccine must be recorded on the CRF for the first 50 subjects in groups 1 and 2 and from all subjects in group 3 (Reactogenicity Cohort). All subjects being followed for solicited AEs will be offered a memory aid to assist in recall of AEs. All unsolicited AEs occurring within 28 days following administration of each dose of vaccine and, where applicable, course of per protocol scheduled anti-malarial treatment, must be recorded on the CRF for all subjects. All SAEs that occur will be collected and recorded from the time the subject consents to participate in the study until she/he is discharged. The occurrence of an AE or SAE may come to the attention of study personnel during study visits and field worker visits. Information to be collected includes event description, date of onset, clinician's assessment of severity, relationship to study product, and date of resolution/stabilization of the event. All AEs occurring while on study must be documented appropriately regardless of relationship. All AEs will be followed to adequate resolution.

Any medical condition that is present at the time that the participant is screened will be considered as baseline and not reported as an AE. However, if the study participant's condition deteriorates at any time during the study, it will be recorded as an AE.

After the initial AE/SAE report, the investigator is required to proactively follow each subject and provide further information per study reporting procedures (section 8.4). All AEs and SAEs documented at a previous visit/contact and designated as not recovered/not resolved or recovering/resolving will be followed-up.

Investigators will follow-up subjects:

- with SAEs or who are withdrawn from the study as a result of an AE, until the event has resolved, subsided, stabilized, disappeared, the event is otherwise explained, or the subject is lost to follow-up;
- or, in the case of other non-serious AEs, until the AE resolves, they complete the study, or they are lost to follow-up.

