8.6. Solicited adverse events

Solicited local and general AEs will be collected among RTS,S vaccinated groups in the first 50 subjects enrolled in Groups 1 and 2 and all subjects enrolled in group 3 (Reactogenicity Cohort) for seven days (day of vaccination and six subsequent days) after each dose of vaccine. On the day of vaccination for each vaccine dose, the evaluation will be carried out by the study clinician at the KCRC. Seven days after each vaccination a field worker will visit each subject and review the memory aid for solicited local and systemic AEs and unsolicited AEs that have occurred since vaccination and per protocol scheduled anti-malarial treatment, if applicable.

Local (injection site) adverse events

- Pain at injection site
- Swelling at injection site

Systemic adverse events

- Fever (temperature $\geq 37.5^{\circ}\text{C}$)
- Headache
- Gastrointestinal problems
- Fatigue
- Muscle ache

The visiting field worker will record these adverse events during the field worker visits.

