10.3.3. Safety analysis population

All subjects in the TVC for which any safety data is available. All safety analyses will be performed using this population. The denominators for different safety endpoints may vary according to the number of subjects with available data for the specific endpoint.

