10.4.4. Safety Analyses

For the safety analysis, data from all subjects from the safety analysis population will be included. All analyses will be descriptive. Data will be presented by dose, overall/dose and overall/subject. Results

will be summarized by study group. The percentage of subjects with at least one AE during the follow-up period will be tabulated with exact 95% CI (two-sided). No multiplicity adjustment will be implemented in analysis. The reports of solicited and unsolicited AEs will be reviewed by a physician and will be categorized by the MedDRA dictionary. The percentage of subjects with at least one report of unsolicited AE and reported up to 28 days after each anti-malarial course will be tabulated with exact 95% CI. The percentage of subjects with at least one report of unsolicited AE and reported up to 28 days after each vaccine dose will be tabulated with exact 95% CI.

The occurrence of SAEs will be determined on the safety analysis population. The proportion of subjects with an SAE, classified by the MedDRA preferred term level, reported from study start until study conclusion will be tabulated with exact 95% CI. Comparisons between groups will be done using Fisher's Exact Test for each preferred term. Serious adverse events (SAEs) occurring at any point during the trial will be summarized and relatedness to vaccine will be assessed.

Withdrawals due to AEs/SAEs will also be summarized. Vital signs which are outside of the normal range and clinically significant will also be listed in tables. The frequency of signs and symptoms will be compared between groups with the chi-square test or Fisher's exact test.

The occurrence of Grade 3 solicited and unsolicited general reactions will be determined on the Total Vaccinated Cohort. The proportion of subjects with a Grade 3 solicited and unsolicited reaction, reported from study start until study conclusion will be tabulated with exact 95% CI. Comparisons between groups will be done using Fisher's Exact Test.

The occurrence of adverse events will be determined on the Total Vaccinated Cohort. The proportion of subjects with an AE, classified by the MedDRA preferred term level, reported from study start until study conclusion will be tabulated with exact 95% CI. Comparisons between groups will be done using Fisher's Exact Test.

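### Section 10.4.4 tests Grade 3 solicited and unsolicited reactions between unnamed groups on the whole vaccinated cohort, but solicited events are captured in only part of Groups 1 and 2 and in no rabies recipient

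*Protocol*

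**What the plan says.** Section 10.4.4 sets the Grade 3 analysis: "The occurrence of Grade 3 solicited and unsolicited general reactions will be determined on the Total Vaccinated Cohort". The measure is "The proportion of subjects with a Grade 3 solicited and unsolicited reaction, reported from study start until study conclusion", tabulated with an exact 95% CI and compared between groups by Fisher's exact test. No groups are named and nothing limits the comparison to subjects followed for solicited events. The next paragraph uses the same population for all adverse events ("The occurrence of adverse events will be determined on the Total Vaccinated Cohort"), again with Fisher tests. It does not say whether solicited reports count.

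Collection is narrower. Section 8.6: "Solicited local and general AEs will be collected among RTS,S vaccinated groups in the first 50 subjects enrolled in Groups 1 and 2", together with all of Group 3. Appendix B, footnote 1, makes clear that the 50 is per group. Section 7.1.1 adds: "Subjects in Groups 4 and 5 will not have solicited AEs captured". Unsolicited events within 28 days of each vaccine dose, and of each scheduled antimalarial course where there is one, "must be recorded on the CRF for all subjects" (section 8.3).

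Section 10.3.3 says of the safety analysis population: "All safety analyses will be performed using this population". It adds: "The denominators for different safety endpoints may vary according to the number of subjects with available data for the specific endpoint".

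**The concern.** The stated comparison does not fit the data that will exist.

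- **One joint proportion.** Every subject has unsolicited follow-up, so the denominator is the whole group. The numerator is fed by solicited reports in all of Group 3, part of Groups 1 and 2, and none of Groups 4 and 5. Rates in Groups 1 and 2 are diluted. The comparisons of Group 1 v 4, 2 v 5 and 3 v 1 partly measure who was asked.
- **Two separate proportions.** The denominator sentence in 10.3.3 gives usable solicited rates in Groups 1 to 3. The between-group test, left unrestricted, still implies a solicited comparison with rabies, for which there are no data.

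At stake is a p-value that could be read as a vaccine effect (Group 1 v 4 or 2 v 5) or as an effect of withholding antimalarial treatment (Group 3 v 1) when it partly reflects ascertainment.

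**Working it through.** **Group sizes (section 10.5.1), reproduced.** Groups 1 and 4: 35 + 129 = 164 each. Group 3: 35. Groups 2 and 5: 256/2 = 128 each. Total: 363 + 256 = 619.

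**Share followed for solicited events.** Group 1: 50/164 = 30.5%. Group 2: 50/128 = 39.1%. Group 3: 35/35 = 100%. Groups 4 and 5: 0/292 = 0%. Overall this is 135/327 = 41.3% of RTS,S subjects.

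**Model for the joint reading.** The protocol gives none of the following rates, so all are assumptions:
- r = true proportion with a Grade 3 solicited-type reaction, the same in every group;
- u = share of such reactions in unasked subjects that still surface as unsolicited events;
- b = background proportion with another Grade 3 unsolicited event.

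P(recorded | asked) = 1 - (1-b)(1-r). P(recorded | not asked) = 1 - (1-b)(1-ru). All randomized subjects are taken as vaccinated, and Fisher's test as two-sided at 0.05.

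**Example: r=15%, b=5%, u=25%.**
- Asked: 1 - 0.95 x 0.85 = 19.2%. Not asked: 1 - 0.95 x 0.9625 = 8.6%.
- Group 1: (50 x 0.1925 + 114 x 0.0856)/164 = 11.8%.
- Group 2: (50 x 0.1925 + 78 x 0.0856)/128 = 12.7%.
- Group 3: 19.2%. Groups 4 and 5: 8.6%.

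The same true rate is thus recorded as anything from 8.6% to 19.2%.

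**Exact probability of p<=0.05 with no true difference.** Each group's count is the sum of two binomials, asked and unasked; all tables are enumerated.

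| Comparison | Assumptions | Probability |
|---|---|---|
| 1 v 4 | r=15%, b=5%, u=0 | 25.4% |
| 1 v 4 | r=15%, b=5%, u=25% | 11.8% |
| 1 v 4 | r=15%, b=5%, u=75% | 4.2% |
| 1 v 4 | r=15%, b=20%, u=25% | 7% |
| 1 v 4 | r=10%, b=5%, u=25% | 7.2% |
| 1 v 4 | r=5%, b=5%, u=25% | 4.1% |
| 2 v 5 | r=15%, b=5%, u=25% | 13.8% |
| 3 v 1 | r=15%, u=25%, b=5% in both | 19.0% |

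With equal capture (u=100%) the test's own rate is 2.6% to 3.7% for 1 v 4 and 2.3% to 3.7% for 3 v 1.

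**Correction for Group 3 v 1.** Equal b is not right here. Group 3 receives no scheduled antimalarials and so has no 28-day windows after them. From the Appendix B and C study days:
- Group 1 unsolicited capture: day -27 to 57 (84 days) plus day 190 to 225 (35 days) = about 119 days.
- Group 3: day 1 to 57 (56 days) plus day 197 to 225 (28 days) = about 84 days.

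The ratio is 119/84 = 1.42, so b=5% in Group 3 corresponds to about 7% in Group 1, and 10% to about 14%. At r=15%, u=25% the probability becomes about 12% (b=5% v 7%) or 6% (b=10% v 14%). At r=10%, u=25%, with 5% v 7%, it is about 7%. At r=5%, with 5% v 7%, it is 3% to 5%. The longer background window in Group 1 partly offsets its weaker solicited capture.

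**After the change.** Group 1 v 3 on solicited data alone (50 v 35), with r from 5% to 20%, gives 1.6% to 3.4%.

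**The case against.** The strongest case against has four parts.

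1. **Section 10.4.4 never defines a composite.** Section 4.2.2 lists solicited (7-day) and unsolicited (28-day) events as separate endpoints, and table layout is left to a statistical analysis plan not seen here. This stands: a reader might infer that a joint proportion is settled, and the text does not establish that. It does not rescue the unrestricted comparison, because Groups 4 and 5 have no solicited data on either reading.
2. **The rates are assumed, and the example favours a visible effect.** This also stands. Nothing in the protocol supports 15% Grade 3 reactions, least of all in rabies recipients. The analysis window runs over three vaccinations and up to three antimalarial courses, so b could well exceed 5%. Reporting by unasked subjects need not be low: the day-2 and day-8 visits after dose 1 are not restricted to the Reactogenicity Cohort, although Visits 12 and 18 are. A limiting case with b=0 and u=0 gives 78% for Group 1 v 4 at r=15%. It would be wrong to present that as the expected size.
3. **The population conflict is nearly nominal.** The safety analysis population is the vaccinated cohort with any safety data, and every vaccinee is observed for at least 30 minutes. A reader might infer that the two labels give different results; they should almost coincide.
4. **The section calls its analyses descriptive.** That limits the weight, but the same section orders Fisher tests, so the p-values will be produced.

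**Conclusion.** The point holds as a mismatch between a stated analysis and the protocol's own collection plan. Capture of 50/164, 50/128, 35/35, 0/164 and 0/128 follows directly from the text. Bias in the Grade 3 rates needs the joint reading. The unsupported solicited comparison with rabies remains on either reading.

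The size is uncertain. For Group 1 v 4 the example gives about 12% false positives, falling to about 4% if most unasked reactions are reported anyway (u=75%) and to 7% with b=20%. There is no inflation at r=5%. For Group 3 v 1 the equal-background figure of 19% overstates the problem; about 6% to 12% is more realistic at r=15%, u=25%.

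A reader might infer that the safety conclusions as a whole are unsound, or that a false signal is likely. The protocol supports neither. This is a secondary, descriptive safety analysis, the efficacy analysis does not use it, and no stopping rule depends on it. Minor to moderate; worth correcting because the correction is cheap.

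**What to change.** Amend section 10.4.4 as follows.

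1. Report solicited events, including Grade 3, in the Reactogenicity Cohort only. Use as denominators the subjects with solicited data (up to 50, 50 and 35), and limit any solicited comparison to Groups 1 to 3.
2. Report Grade 3 unsolicited events separately on the safety analysis population. For comparisons involving Group 3, count only the 28-day windows after vaccination, because Group 3 has no post-antimalarial windows.
3. State that the all-event Fisher comparison with Groups 4 and 5 excludes solicited reports.
4. Name the safety analysis population instead of the Total Vaccinated Cohort, to agree with 10.3.3. This is for consistency and is unlikely to change any number.

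The cost is a few sentences and the matching table shells, with no change to data collection. There will be no solicited comparison with rabies, which the collection plan already rules out.

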10.4.5. Adherence and Retention Analyses

Participants who prematurely discontinue from the study will not be included in analyses/summary statistics beyond the time of discontinuation.

Rates of discontinuation and reason for discontinuation will be summarized in data listings or summary tables.

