2.3. Potential Risks and Benefits

Details of potential risks are provided in the Investigator's Brochure for RTS,S/AS01. Potential risks for licensed products to include DHA/Pip, Coartem[®], Primaquine, and Abhayrab[®] are included below and details may be found in the package insert for the product.

As indicated in section 5.2, pregnant women are excluded from participating in the vaccination portion of this study. While pregnant women and their fetuses are particularly susceptible to the effects of *P. falciparum* malaria, this study will exclude women who are pregnant at the time of screening, or who become pregnant during the immunization phase of the study for two reasons. First and foremost, the safety of the RTS,S/AS01_E vaccine (intended for immunization of young children 5-17 months of age only) has not been previously evaluated in nonclinical reproductive toxicology studies by GSK. This requirement for nonclinical toxicology is recommended in the draft FDA guidance document on the inclusion of pregnant women in clinical trials (<https://www.fda.gov/regulatory-information/search-fda-guidance-documents/pregnant-women-scientific-and-ethical-considerations-inclusion-clinical-trials>).

Secondly, the current study is an experimental medicine study to examine whether immune hyporesponsiveness to a model CS-based vaccine (in this case RTS,S/AS01_E) is observed in adults who may or may not be infected with *P. falciparum* parasites at the time of immunization. The study is not intended to support a clinical development plan for regulatory approval in either adult men or women.

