5.4. Participant Withdrawal or Termination

5.4.1. Reasons for Withdrawal or Termination

Subjects can leave the study at any time for any reason if they wish to do so without any penalty or loss of benefits to which they are otherwise entitled. Subjects can also be withdrawn from the study procedures at the discretion of the clinical investigator. The following reasons may lead to withdrawal of individual subjects:

- Withdrawal of informed consent by volunteer;
- Any serious adverse event;
- Any adverse event that, according to clinical judgment of the investigator, is considered as a definite contraindication to proceeding with the study procedures;
- Completely lost to follow-up (unable to contact after at least 3 phone or physical attempts by the study staff to locate the participant and 1 in-person attempt by a field supervisor to contact the individual; additional attempts may be made at the discretion of the PI);
- Pregnancy during immunization phase
- Ineligibility (arising during the study or retrospectively, having been overlooked at screening);
- If the investigator or DoD Research Monitor believes that continuation would be detrimental to the subject's well-being;
- Volunteer non-compliance with study requirements;
- Any other protocol deviation that results in a significant risk to the subject's safety.

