5.4.2. Handling of Participant withdrawals or termination

Investigators, or designee, will follow subjects who are withdrawn as result of a SAE/AE until resolution of the event and/or chronicity is established. Study staff will make an attempt to contact those subjects who do not return for scheduled visits or follow-up. Information relative to the withdrawal will be documented on the CRF. The investigator will document whether the decision to withdraw from the study was made by the subject or the investigator and which of the following possible reasons was responsible for withdrawal:

- serious adverse event
- non-serious adverse event
- protocol violation (specify)
- consent withdrawal, not due to an adverse event
- moved from the study area
- lost to follow-up

If a subject withdraws or is terminated from the study after enrolment and receipt of investigational product (including anti-malarial medications), including lost to follow-up, they will not be replaced. If a subject withdraws or is terminated from the study after enrolment but prior to receipt of investigational product, including lost to follow-up, (e.g., participant in group 3 who withdraws or is terminated between study visits 2 and 5) that participant may be replaced.

If the reason for withdrawal from the study is pregnancy during the immunization phase of the study, the participant will be withdrawn from any further immunizations, but will be followed for safety until delivery or termination of the pregnancy.

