8.4.4. Reporting of Pregnancy

Subjects who become pregnant during the study must not receive additional doses of investigational study vaccines but may continue other study procedures at the discretion of the investigator. The investigator, or his designee, will collect pregnancy information on any subject who becomes pregnant while participating in this study. The investigator, or his designee, will record pregnancy information on the Pregnancy Report Form and submit it to the WRAIR IRB, KEMRI SERU, Kenya PPB, PATH, and GSK. In

the event a woman becomes pregnant after completing all three vaccinations she will be eligible to continue in the ADI phase. If a pregnant female develops asymptomatic malaria infection discovered by a positive malaria PCR during ADI, she will be treated with standard of care malaria therapy.

The subject will be followed to determine the outcome of the pregnancy. At the end of the pregnancy, whether that be full-term or premature, information on the status of the mother and child will be forwarded to the above ethical committees, regulatory authorities and sponsor for reporting.

While pregnancy itself is not considered an AE or SAE, any pregnancy complication or elective termination of a pregnancy for medical reasons will be recorded as an AE or a SAE. A spontaneous abortion is always considered to be a SAE and will be reported.

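### Section 10.4.5 cuts discontinued participants out of analyses with no safety exception, which conflicts with the whole-study SAE analysis and the safety follow-up required after withdrawal

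*Protocol*

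**What the plan says.** The rule is in Protocol section 10.4.5, Adherence and Retention Analyses: "Participants who prematurely discontinue from the study will not be included in analyses/summary statistics beyond the time of discontinuation". It names no endpoint and carves nothing out.

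Other sections bear on the same data:

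- **Section 5.4.1** lists reasons that may lead to withdrawal. They include any SAE, an adverse event judged a contraindication, and "Pregnancy during immunization phase".
- **Section 5.4.2** says that investigators "will follow subjects who are withdrawn as result of a SAE/AE until resolution of the event and/or chronicity is established". Where pregnancy in the immunization phase is the reason for leaving the study, "the participant will be withdrawn from any further immunizations, but will be followed for safety until delivery or termination of the pregnancy".
- **Section 8.3** repeats the duty to follow participants with SAEs, and those withdrawn because of an adverse event, until the event settles. It collects SAEs from consent to the participant's discharge.
- **Section 8.4.4** requires pregnancies to be followed to outcome and adds: "A spontaneous abortion is always considered to be a SAE and will be reported". It also lets pregnant participants carry on with other study procedures if the investigator agrees.
- **Section 10.4.4** bases the safety analysis on everyone in the safety population. It tabulates SAEs from the start of the study to its end, summarizes SAEs whenever in the trial they occur, and also summarizes withdrawals for adverse events.
- **Section 4.2.2** defines the SAE endpoint as the count and proportion of participants with SAEs over the entire study.

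**The concern.** Stopping the clock at discontinuation is ordinary for a time-to-infection endpoint. For safety it is not, because the protocol goes out of its way to keep collecting safety data after withdrawal. If the 10.4.5 sentence governs the safety tables, those data are collected and reported to the ethics committees and the regulator but do not reach the trial's own SAE results.

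The clearest exposure is pregnancy. Section 2.3 gives as a reason for excluding pregnant women that the safety of the vaccine "has not been previously evaluated in nonclinical reproductive toxicology studies by GSK". A miscarriage after exposure is the kind of event that a reader of the safety results would want to see counted.

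The trial is open label (section 7.1.1). If the conflict is left standing, the choice between the two readings could be made by people who know which group the events fall in.

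**Working it through.** No stated figure is at issue, so the check is a comparison of passages, followed by a bound on scale.

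**Step 1: do 10.4.4 and 10.4.5 conflict?** Section 10.4.4 fixes who is analysed (the whole safety population) and the calendar window (study start to study end). Section 10.4.5 fixes how far an individual's data run. They can be combined as every vaccinated participant, truncated at discontinuation. They can also be read with 10.4.4 as the specific rule that prevails for safety. The window in 10.4.4 and the endpoint in 4.2.2 favour the second reading, but neither says whether a withdrawn person still counts as in the trial. No order of precedence is given.

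**Step 2: which events depend on the reading?**

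| Event | Timing relative to discontinuation | Under literal 10.4.5 |
|---|---|---|
| SAE that causes withdrawal | Before | Still counted in the SAE proportion and in the summary of withdrawals |
| Later or fatal outcome of that SAE | After | Proportion of participants unchanged; outcome could go unsummarized |
| Miscarriage after withdrawal for pregnancy | After | Left out, although an SAE under 8.4.4 |
| New, unrelated SAE after withdrawal | After | Left out if collected; 5.4.2 and 8.3 do not clearly require its collection |

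**Step 3: is pregnancy a discontinuation?** Section 5.4.2 speaks first of withdrawal from the study and then of withdrawal from further immunizations. Section 8.4.4 allows other procedures to continue. So some pregnancies will be discontinuations and others will not. Only the former fall under 10.4.5.

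**Step 4: scale.** Section 10.5 assumes 10% dropout: 619 × 0.10 = 61.9, so about 62 participants could come under the rule. This is a ceiling on those planning figures. Some would leave before any vaccination and so lie outside the safety population, and many would have no safety data after leaving. The protocol gives no rate of SAEs or pregnancies after withdrawal.

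A range for miscarriage alone needs inputs that are all **assumptions**: half of the 327 RTS,S recipients (164 + 128 + 35) are women who can conceive, 3–8% conceive in the immunization phase, 10–15% of those miscarry, every pregnancy is treated as a discontinuation, and 2–5% of participants have an SAE.

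- Pregnancies: 164 × 0.03 = 4.9 to 164 × 0.08 = 13.1.
- Miscarriages: 4.9 × 0.10 = 0.5 to 13.1 × 0.15 = 2.0.
- Participants with an SAE: 327 × 0.02 = 6.5 to 327 × 0.05 = 16.4.
- Ratio: 0.5 / 16.4 = 3% to 2.0 / 6.5 = about 30%.

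The top of that range pairs the highest miscarriage count with the lowest SAE count. Contraception is an entry requirement for women of childbearing potential (section 5.1), and not every pregnancy is a discontinuation. Both pull the count down, and zero or one affected event is quite possible.

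**The case against.** The strongest reply is that 10.4.4 is the section on safety and already points to inclusion, while the disputed sentence sits under an adherence and retention heading and mentions no safety endpoint. On that view there is nothing to lose, only a loose sentence. This stands in part: loss of safety data is one literal reading, not a settled consequence. It does not remove the conflict, because the sentence speaks of analyses generally and nothing ranks it below 10.4.4.

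A reader might infer three stronger things that the documents do not support:

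- **That the SAEs which drive people out of the trial disappear.** They do not. They begin before discontinuation and stay in the numerator.
- **That every pregnancy in the immunization phase is cut.** Section 5.4.1 lists reasons that may lead to withdrawal, and 8.4.4 permits continued participation.
- **That the comparisons between groups are biased.** The same rule applies to the rabies vaccine groups, 10.4.4 calls its analyses descriptive, and no material effect on its Fisher tests by preferred term can be shown from the documents.

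The events would also still reach oversight through the expedited reports in 8.4 and the research monitor in 8.5. That protects participants during the trial, but it does not put the events into the final safety tables.

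**Conclusion.** The point holds as an unreconciled conflict. Section 10.4.5 has no safety exception, and it contradicts the safety analysis in 10.4.4, the whole-study SAE endpoint in 4.2.2, and the purpose of the follow-up after withdrawal in 5.4.2 and 8.3. Taken at its word, it would omit SAEs first arising after withdrawal, miscarriage being the clear case, and the later course of SAEs that led to withdrawal.

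The number of events is unknown and probably small; the 3–30% range rests entirely on assumed rates. It would be wrong to conclude that safety data will certainly be lost or that the SAE results are certainly understated. The conflict should be fixed because the rule is stated rather than merely missing, the affected events matter individually, and the correction costs almost nothing. It does not threaten the validity of the trial.

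**What to change.** 1. In 10.4.5, limit the sentence to the efficacy and immunogenicity analyses, with efficacy follow-up censored at discontinuation.
2. In 10.4.4, state that SAEs, adverse events of special interest, deaths and pregnancy-related SAEs actually collected after withdrawal under 5.4.2, 8.3 and 8.4.4 are included in the safety summaries by group.

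The cost is two sentences, carried into the statistical analysis plan. No new data collection follows, because the second sentence covers only what is collected anyway. A separate listing of pregnancy outcomes by group and last dose received would be a useful option, but its absence is not an error in the protocol.
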